**b. Procedures for obtaining informed consent**

A member of the study staff will determine patients' eligibility status, explain the purpose of the study and study procedures, and answer any questions prior to completing informed consent per the information below.

Patients will be provided with the informed consent document electronically or via paper mail. The informed consent document will be carefully reviewed with study staff via discussion with the patient either by phone or videoconference. Patients who are recruited while inpatient may also have the option to complete consent in person. The consent form will include a description of all study procedures and information about potential risks and benefits of participation. It will state that participation is voluntary, that participants can refuse to answer questions that make them uncomfortable, that participants can discontinue participation at any time, and that not completing the study will not compromise their medical care. Special attention will be given during the consent process to the implications of the study design (e.g., randomization) and of receiving an intervention or educational information online via videoconferencing services. Subjects will be explicitly informed that videoconferencing services provide secure HIPAA-compliant videoconferencing software. We will explain to participants that although we will do our best to ensure confidentiality on our end, there is still a potential risk of loss of confidentiality. Participants will also be advised to wear headphones and sit in a quiet place to protect their own, and other group members' privacy.

After the form is reviewed and all of the patient's questions have been answered, the patient may then sign and submit the form electronically or via paper mail. All patients will be provided with study staff contact information if any questions or concerns regarding the research arise.

As stated above, member of the study staff will obtain informed consent in one of three ways, depending on patient preference: 1) electronically (via REDCap or emailed pdf of the consent form), 2) via paper mail correspondence, or 3) in

person (for patients who are recruited while inpatient). Participants who opt to receive the consent materials via paper mail will be asked to provide a mailing address. Participants who opt for electronic consent will be made aware of security concerns related to email communication (as described earlier) and, after specifying their preference for encrypted or unencrypted email, be emailed the informed consent portal via REDCap or electronic copy of the consent form.

*REDCap Electronic Informed Consent Process (EIC):*

Participants who choose to complete the consent form electronically will be emailed a link for the informed consent portal via REDCap. The REDCap link will connect the participant to an encrypted REDCap portal; the Electronic/Paperless Consent Template Project will be used. Once the participant confirms receipt of the EIC form link, they will be prompted to enter in their full name and birthday to access the informed consent form and verify their identify. This portal will have the electronic (paperless) consent form, exactly identical in content to the paper version, to guide the participant through the consent discussion with study staff over the phone. The participant will be given ample opportunity to ask questions and take their time to consider their participation. If a participant would prefer, they may return to the EIC portal as many times as they would like to review the consent form on their own time. When ready to sign consent, participants will digitally sign and date/time the consent form.

Additionally, the participant will be prompted after signing to indicate the method through which they would like to receive a copy of the consent form for their record: digitally or through hard copy. If a participant would like to receive a copy of the consent form digitally, they will be asked their preference to receive the email as encrypted, the default, or opt-out and receive the email unencrypted. These options allow participants to be informed of what an encrypted (Send Secure) email would appear as in their inbox and the steps to get into the email, or alternatively, to give permission to receive the email without this extra layer of security but in a more accessible format. Partner's Healthcare language concerning the Send Secure feature is included to assist in this decision. Study staff will confirm receipt of the digital signature and will sign and date the consent form as the consenting study staff member. At any point, if a participant would prefer to receive a hard copy of the consent form, the EIC process will stop, and study staff will commence the phone and mail correspondence process for informed consent.

*Paper Mail Correspondence*

Participants may also elect to receive an electronic copy (pdf) of the consent form via email, according to the email security procedures previously described. In this case the participant could print and sign the form and either scan/email or send via paper mail back to the research team.

If the participant would prefer to complete the informed consent process via paper mail, study staff will start by facilitating the informed consent discussion over the phone. Once all questions are answered to the satisfaction of the participant, study staff will mail 2 signed copies of the informed consent form for the participant to review, sign and mail back one copy at their convenience. Participants will be provided with a pre-stamped, pre-addressed envelope for their return. Study staff will maintain one copy of the informed consent form for study records, participants will be instructed to maintain one copy for personal reference.

*In-person Informed Consent Process*

Study staff will go through the informed consent discussion in a hospital or private room to protect patient confidentiality and answer any questions. Upon consent, study staff will maintain one copy of the informed consent form for study records, and participants will be instructed to maintain one copy for personal reference. Patients who would like more time to consider participation are able to take the forms home with them to review, and if interested, they may complete the consent process electronically or proceed to mail back the consent forms.

Following consent, the participant will be asked to provide and clarify their preferred contact modalities for their participant throughout the study. They will be informed that they can change these preferences at any time. Study staff will document the outcome of this conversation and proceed with participant contact accordingly.

**c. Treatment assignment and randomization**

Participants will be randomized to a MBCT or a time- and attention-matched health enhancement control in a 1:1 design using a random number generator.

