## II. SPECIFIC AIMS

- a. Aim 1:** To establish, in a pilot RCT (approx. N=50 participants) with a time- and attention-matched health enhancement control, (a) the feasibility of the recruitment procedures (screening, eligibility, enrollment rates), and feasibility and acceptability of the (b) MBCT and control interventions (adherence, retention, fidelity, satisfaction, group videoconferencing delivery) and (c) data collection procedures by group (adherence, satisfaction). Hypothesis 1a: Recruitment will be feasible as evidenced by screening, eligibility, and enrollment rates; (1b) the MBCT and control interventions and (1c) data collection procedures in both groups will be feasible and acceptable.
- b. Aim 2 (exploratory):** To explore within-group changes in psychosocial and physical health outcomes following virtual MBCT and the control intervention (e.g., depression, inflammation, emotion regulation, pro-sociality, and health behaviors).

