**V. STUDY PROCEDURES**

**a. Study visits and parameters to be measured**

*Adapted MBCT intervention*

The MBCT intervention is based on Mindfulness-Based Cognitive Therapy (MBCT), an evidence-based, manualized protocol for treating depression symptoms. We have developed an adapted MBCT protocol based on our preliminary qualitative work and open pilot trial and continue to make iterative refinements based on patient feedback. Participants randomized to the MBCT intervention will be expected to participate in 8-weekly virtual sessions, in conjunction with approximately 30 minutes of at-home daily practice. Each weekly virtual session will last approximately 1.5 hours. A licensed mental health provider (e.g., LICSW, PhD) trained in the MBCT protocol will deliver the

intervention. The interventionist will receive ongoing supervision and feedback from the PI or MBCT mentor. The MBCT intervention will not be delivered clinically; it is a psycho-educational intervention. We will also send audio recordings used for home mindfulness practice via Partners email (send secure or unencrypted if the patient prefers).

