#### *Health Enhancement Control Group*

The control intervention will be a group videoconferencing program focused on depression and cardiac health education (e.g., relationship between depression and cardiac health, cardiac risk factors, cardiac health behaviors, finding resources for mental health care). It will follow the same structure as MBCT but will not contain mindfulness practices or psychoeducation. Participants randomized to the health enhancement control group will be expected to participate in 8-weekly virtual sessions, where each session will last approximately 1.5 hours. To promote equivalent between-session practice, participants will identify health behavior goals to work on and track over the week. A licensed clinician or pre-doctoral or post-doctoral fellow with supervision from a licensed clinician will lead the control group.

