#### *Home practice logs*

Only the intervention group will receive weekly home practice logs. Prior to each session participants will be asked to email, mail, or complete via REDCap a record of their at-home mindfulness practice since the previous session. The home practice logs are included in the IRB submission.

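### The control's time match holds for sessions (12 h per arm), but between sessions it is neither specified nor measured, because only MBCT has a stated practice time and a practice log

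*Combined protocol and SAP*

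**What the plan says.** Section II (Aim 1) sets up the pilot "with a time- and attention-matched health enhancement control", and section IV.c repeats the description: participants are assigned to MBCT or a "time- and attention-matched health enhancement control in a 1:1 design". Neither place defines the term or says whether it covers work done at home.

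Section V.a gives the content of each arm.

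- **MBCT:** participants are expected to take part in "8-weekly virtual sessions, in conjunction with approximately 30 minutes of at-home daily practice". On length, "Each weekly virtual session will last approximately 1.5 hours". Audio recordings for home use are sent by email.
- **Control:** the number and approximate length of sessions are the same, the format is again group videoconference, and the program follows MBCT's structure without the mindfulness content. Between sessions, "participants will identify health behavior goals to work on and track over the week". The section says that the purpose is to make between-session practice equivalent. It gives no minutes and no frequency.
- **Recording:** "Only the intervention group will receive weekly home practice logs".

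Table 1 (section VI.a) has a row for the MBCT and control interventions together. One benchmark in that row is that at least 75% complete home practice on 3 or more days a week.

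**The concern.** The protocol treats between-session work as something to equate across arms, but it states an amount for one arm only and collects a log from that arm only. Home practice is most of the expected MBCT time, so the unmeasured part is larger than the part known to match.

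Two things are at stake. First, Aim 1 is to establish feasibility and adherence for both interventions. As described, the pilot would end without knowing how much between-session work control participants did, and the Table 1 home-practice benchmark would have no log behind it in that arm. Second, section VIII.b says that the study will inform a later efficacy trial. In that trial, a time-matched control is what would let a difference between arms be attributed to content rather than to hours spent. The later trial would inherit a matching claim that the pilot could have tested and did not.

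**Working it through.** The documents state no total-hours figure, so there is none to reproduce.

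**Inputs (section V.a).** Both arms: 8 sessions of about 1.5 h. MBCT home practice: about 30 minutes (0.5 h) a day. Control home time: not stated. The practice period is taken as 7 weeks (the intervals between 8 weekly sessions) or 8 weeks.

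**Sessions.** 8 × 1.5 = 12 h in each arm. These match.

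**MBCT home practice.** 0.5 × 7 × 7 = 24.5 h, or 0.5 × 7 × 8 = 28 h.

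**MBCT total.** 12 + 24.5 = 36.5 h, or 12 + 28 = 40 h. The share outside sessions is 24.5/36.5 = 67%, or 28/40 = 70%.

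**Control total.** This cannot be computed. The table varies control goal work over an assumed range of 0 to 30 minutes a day. Control home hours are (minutes/60) × 7 × weeks. The excess is MBCT home hours minus control home hours, and the ratio is MBCT total over control total. Each cell gives 7 weeks, then 8 weeks.

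| Assumed control min/day | Control home h | MBCT excess h | Ratio of totals |
|---|---|---|---|
| 0 | 0; 0 | 24.5; 28.0 | 36.5/12 = 3.04; 40/12 = 3.33 |
| 10 | 8.2; 9.3 | 16.3; 18.7 | 36.5/20.2 = 1.81; 40/21.3 = 1.88 |
| 20 | 16.3; 18.7 | 8.2; 9.3 | 36.5/28.3 = 1.29; 40/30.7 = 1.30 |
| 30 | 24.5; 28.0 | 0; 0 | 1.00; 1.00 |

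**At the Table 1 benchmark.** If MBCT participants practiced on 3 days a week for 30 minutes each time (the minutes are an assumption here), home practice would be 0.5 × 3 × 7 = 10.5 h, or 0.5 × 3 × 8 = 12 h.

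**What is recorded.** Sections V.a and V.e describe logs for the MBCT arm only. Section V.e says that those logs cover how often participants practice and their thoughts about it, and does not mention minutes. Control participants track their goals, but no section says that the tracking is collected. The post-session surveys are described as covering perceptions, likes and dislikes. So no described instrument yields between-session time in control, and it is not clear that one yields minutes in MBCT.

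**The case against.** The strongest reply is that the label is not wrong. The documents do not define it, and on the ordinary reading of leader-delivered contact the arms do match: same number of sessions, same length, same format and same structure. The protocol also gives control participants between-session work with the stated aim of equivalence. This reply stands against anyone who infers that the control is simply not time-matched. Undefined scope and unstated control time do not make the description false.

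A reader might also infer that MBCT takes about three times as long. That divides MBCT sessions plus home practice by control sessions alone, and so counts unstated control time as zero. The ratio of 3.0 to 3.3 is only the top of the assumed range.

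A third inference, that nothing collected could reveal control time, also goes too far. The survey forms and logs are in the IRB submission, which is not part of these documents, and exit interviews might touch on the subject. What can be said is that the protocol describes no between-session time record for control.

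Finally, no planned result needs the match. Section VI.c describes feasibility outcomes with frequencies and proportions and looks at within-group change. It compares adherent with non-adherent participants from each group but specifies no test between arms. This stands, and it limits the weight of the point.

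The objection does not remove the mismatch between aim and measurement. Section V.a sets equivalence between sessions as a goal, and the rule giving logs to MBCT alone leaves that goal unchecked.

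**Conclusion.** The point holds in a limited form. The match on number and length of sessions is sound at 12 h per arm. The match outside sessions is neither specified nor measured. The MBCT excess lies between 0 and 28 h on the assumed control range of 0 to 30 minutes a day. The upper end, 24.5 to 28 h, is reached only if control goal work takes no time. These figures are prescribed time and rest on MBCT participants practicing daily for 7 or 8 weeks. Actual practice may be lower in either arm.

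No pilot analysis is invalidated. This is a cheap improvement, worth making now because feasibility of the comparator is part of Aim 1 and because a control item cannot be added once the groups have finished.

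**What to change.** 1. Give control participants a short weekly item on days and minutes of goal work, on the same schedule as the MBCT log.
2. Make sure that the MBCT log records minutes as well as days.
3. In section VI.c, add a descriptive report by arm of session time, between-session time and their total. No test is needed.
4. In sections II.a and IV.c, limit the matching claim to number and length of sessions, unless the recorded between-session time supports more.

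The cost is wording in a few sections, one or two weekly items for control and possibly one more field in the MBCT log. The downside is a small added weekly burden for control participants and a less favourable description of the control. Neither arm's intervention content has to change.

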**V. STUDY PROCEDURES**

**a. Study visits and parameters to be measured**

*Adapted MBCT intervention*

The MBCT intervention is based on Mindfulness-Based Cognitive Therapy (MBCT), an evidence-based, manualized protocol for treating depression symptoms. We have developed an adapted MBCT protocol based on our preliminary qualitative work and open pilot trial and continue to make iterative refinements based on patient feedback. Participants randomized to the MBCT intervention will be expected to participate in 8-weekly virtual sessions, in conjunction with approximately 30 minutes of at-home daily practice. Each weekly virtual session will last approximately 1.5 hours. A licensed mental health provider (e.g., LICSW, PhD) trained in the MBCT protocol will deliver the

intervention. The interventionist will receive ongoing supervision and feedback from the PI or MBCT mentor. The MBCT intervention will not be delivered clinically; it is a psycho-educational intervention. We will also send audio recordings used for home mindfulness practice via Partners email (send secure or unencrypted if the patient prefers).

#### *Health Enhancement Control Group*

The control intervention will be a group videoconferencing program focused on depression and cardiac health education (e.g., relationship between depression and cardiac health, cardiac risk factors, cardiac health behaviors, finding resources for mental health care). It will follow the same structure as MBCT but will not contain mindfulness practices or psychoeducation. Participants randomized to the health enhancement control group will be expected to participate in 8-weekly virtual sessions, where each session will last approximately 1.5 hours. To promote equivalent between-session practice, participants will identify health behavior goals to work on and track over the week. A licensed clinician or pre-doctoral or post-doctoral fellow with supervision from a licensed clinician will lead the control group.

#### *Data collection*

For both the intervention group and control group study assessments include a battery of self-report surveys administered at baseline, post-intervention, and 3-month follow-up; session satisfaction surveys administered after each intervention session; post-intervention individual exit interviews (conducted via telephone or videoconference); blood spot samples self-collected by participants at baseline, post-intervention, and 3-month follow-up (submitted to the research team via paper mail). The intervention group will complete home practice logs submitted between each intervention session. Surveys and home practice logs may be completed via REDCap, email, paper mail, phone, or videoconferencing depending on patients' preferences. Data collection will also consist of viewing and extracting data from the EHR to assess medical and demographic variables (e.g. medical diagnoses, medications, cardiac rehab attendance) and/or confirm eligibility. REDCap is a secure online data collection system.

#### *Survey measures*

The self-report survey measures will be the same for the MBCT and control groups. The surveys will be administered within approximately 1-2 weeks before and after the intervention and at 3 months post-intervention. This battery will include the following validated self-report surveys: Assessment of Survivor Concerns (fear of recurrence), CAMS-R (mindfulness), Cardiac History and Symptoms, Current Experiences Scale (CES; resiliency), COVID items,

demographic questionnaire, Expectancy Questionnaire, Experiences Questionnaire (decentering), Group cohesion scale, Hospital Anxiety and Depression Scale (HADS; depression and anxiety), Interpersonal Reactivity Index (IRI; empathy), MAIA-2 body subscales (interoception), MBCT-AS Checklist (fidelity checklist), PHQ-9 (depression), Medical Outcomes Study – Specific Adherence Scale (MOS-SAS; health behaviors), one item from the Short Form-12 (SF-12), Self-Other Four Immeasurables (SOFI; self and other compassion), PROMIS Physical Function (PROMIS-PF; physical function), and The Positive and Negative Affect Schedule-Positive Affect (PANAS-PA). The post-intervention survey will also include a group cohesiveness measures to assess perceived connection with other group members as well as intervention satisfaction questions to assess acceptability. The 3-month follow-up survey will include questions about continued mindfulness practice. The baseline survey, post-intervention survey and post-intervention survey will all include questions related to COVID-19. All three survey batteries are included in the IRB submission.

#### *Post-session surveys*

Both intervention and control group participants will receive post-session surveys. The post-session surveys will be administered immediately after each of the 8-sessions and will assess participants' perceptions, and likes and dislikes, of specific intervention or control group components. The post-session surveys for both the control and intervention group are included in the IRB submission.

#### *Home practice logs*

Only the intervention group will receive weekly home practice logs. Prior to each session participants will be asked to email, mail, or complete via REDCap a record of their at-home mindfulness practice since the previous session. The home practice logs are included in the IRB submission.

#### *Exit interview*

Upon completion of the intervention, participants from both the intervention and control group will be asked to complete a 30-60-minute exit interview via phone or videoconference. These interviews will be audio- and/or video-recorded for transcription.

#### *Dried blood spots*

Both intervention and control group participants will be asked to provide dried blood spot samples. Within one week before and after the intervention and 3-months-post intervention, participants will be asked to provide self-collected whole dried blood spots to assess IL-6, CRP, and TNF- $\alpha$ .

